## 2. Study Objectives

To demonstrate that the proposed approach to measuring SPECT MBF can be applied routinely in a clinical setting and produce consistent data with minimal reduction in patient throughput.

To explore optimization of the acquisition using 1) early imaging post-stress instead of delayed imaging and 2) half-data instead of full-data acquisitions (leading to half dose MBF radiotracer studies).

## 3. Study Design

Patients will be recruited from those referred to the local site's Diagnostic Imaging Department for SPECT myocardial perfusion imaging (MPI) and who have an intermediate to high pre-test likelihood of disease (Diamond-Forrester criteria ≥ 30%). Research imaging will consist of a SPECT acquisition at the time of rest and stress radiotracer injection in addition to the standard (delayed) clinical stress/rest SPECT scan with 99mTc-tetrofosmin. This is an observational study; patients will be managed according to the standard clinical care of the local site. Where available, a CT scan will also be acquired for attenuation and/or scatter correction. Studies may be one day (rest/stress or stress/rest) or two day (rest and stress on separate days)

Study end will be defined as completion of all SPECT imaging at rest and stress.

A core lab will be established at the University of Ottawa Heart Institute. Initial studies acquired at the local site according to the protocol will be evaluated for technical image quality (e.g. patient positioning, CT-SPECT coregistration, noise levels, patient motion and motion correction, artifacts). The core lab will work with local sites, as needed, to implement the protocol and ensure adequate data quality. All studies will be analyzed locally but the raw data will also be anonymized and forwarded to the core facility for reprocessing. Central processing will allow comparison between sites and the repeat processing will provide an estimate of inter-operator variability in the measurements. The core lab will also compare the relative perfusion from immediate and delayed imaging for image quality and diagnostic accuracy (visual and quantitative).

Studies will be acquired at 6 initial sites with mixed prior experience at MBF imaging, to demonstrate feasibility of use in a clinical setting. Each site will acquire 5 studies during an initial start-up period to become comfortable with the SPECT MBF protocol for data acquisition and processing. Studies acquired during the start-up period will not be used in the final analysis but will be processed by the core lab and used to evaluate site training. Following the start-up period, each site will acquire 25 studies within 60 working days to show that the protocol can be implemented without major disruption to clinical throughput.

## Timeline (12 months):

For each site, we anticipate 2-3 months for protocol approval by local ethics committees, 1-2 month for local site training and initial training studies, 2 months for feasibility study acquisitions. We will stagger the entry of sites into the study to facilitate "one-on-one" consultation between the core (Ottawa) site and local sites during initial training period. Reprocessing of local data sets by the core lab will be ongoing with final review and analysis of results during the last quarter.

## 4. SPECT MBF Imaging with Tetrofosmin

## 4.1 Camera

The camera used in this study will be the Discovery NM 530c (GE Healthcare, Haifa, Israel). This camera is a dedicated cardiac camera that uses 19 cadmium-zinc-telluride (CZT) based detectors . Each detector is 8 x 8 cm divided into a 32x32 array with a pixel pitch of 2.46mm. Each detector has a single-pinhole collimator with an effective diameter of 5.1mm. The detectors are arranged in an arc around the field-of-view, providing sufficient angular sampling for 3D reconstruction without the need to rotate the camera. The sensitivity of the system is approximately 4-times higher than a standard dual-head gamma camera.

## 4.2 Patient Preparation

Patient preparation will be the same as for a standard clinical myocardial perfusion study. Participants will be instructed to fast per local procedures (3 hours per ASNC guidelines), and to abstain from products containing caffeine for no less than 12 hours prior to imaging.

## 4.3 Radiotracer

The tracer to be used is 99mTc-tetrofosmin. 99mTc-tetrofosmin will be mechanically delivered using a syringe pump at a constant rate over a 30 s period, followed immediately by a saline flush at the same injection rate as the tracer. The volume of the saline flush should be greater than the volume of the lines connecting the pump to the patient to ensure that the full tracer activity is delivered. There should be no delay between tracer and saline flush injections. Manual injection of radiotracer will not be used for this study to increase standardization but will be evaluated in future studies.

The measurement of CFR with CZT SPECT has been validated with full doses of radiotracer but is most likely possible with half doses. For this feasibility study, full doses will be used to provide the best CFR results possible. The listmode data from the full-dose studies with be reprocessed by the core laboratory to simulate half doses and

confirm that half doses are adequate. The planned subsequent studies of diagnostic accuracy and prognosis would evaluate half doses.

The activity of the radiotracer injected at stress and rest will be full clinical doses with a minimal activity of 370 MBq for the first study and 1100 MBq for the second study for a one day protocol. Injected doses will be 370 MBq at both rest and stress for 2-day protocols.

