## 1.2 Hypotheses

- a) Primary hypotheses
- 1. Feasibility: It is practical to obtain reliable SPECT measurements of MBF routinely within the workflow of a standard clinical practice.
- 2. MBF reproducibility: Global MBF measured at remote sites will agree within 10% with the same data processed at an expert core laboratory.
- b) Secondary hypotheses
- 1. Impact on throughput: Routine implementation of a SPECT MBF protocol will have at most minimal impact on patient throughput (defined as <10% reduction in patient volumes).
- Delayed imaging: static reconstruction of the last 6 min of the dynamic acquisition will provide images that are clinically equivalent (less than 10% change in patient diagnosis from normal (summed stress score < 4) to abnormal or vice versa), compared to standard static images obtained following a 45-min delay post-injection.
- 3. Half-dose MBF measurement: The difference between MBF measurements with full-data and half-data dynamic acquisitions will be less than or equal to the inter-observer variation in MBF measurements with full-data.

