## 4.5 Image Processing and Analysis

Following acquisition, the listmode data will be rebinned into 9x10s, 6x15s, 4x120s frames. The projection data for each frame will be independently reconstructed using manufacturer supplied MLEM iterative reconstruction that includes point-spread function modeling and a noise-suppression prior. A total of 60 iterations will be used corresponding to the manufacturer recommendation for resting (low-count) studies. Images will be filtered post-reconstruction using a 3D 5th-order Butterworth filter with a cut-off frequency of 0.37 cycles/cm. Images will be reconstructed without corrections (NC), and with attenuation correction (AC) when a CT attenuation scan is available. When applied, AC will be based on a CT scan acquired separately with the patient on the same configuration as used for the SPECT dynamic acquisitions.

The reconstructed dynamic image series will be processed using the kinetic analysis software tools provided by the manufacturer (GE Healthcare). With this semi-automatic software, a 1-tissue-compartment model will be fit to the myocardium time-activity data to generate a parameterized map of the uptake rate constant K1 (ml/min/g) for the heart. K1 values will be scaled to MBF based on the K1-MBF relationship determined from previous single-site comparisons of clinical SPECT and Rb82 PET studies .

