## 5. Sample Size and Analysis

Adverse events will be listed on an individual basis. All safety variables and demographic data will be tabulated with descriptive statistics, if appropriate.

Bland-Altman plots will be used to determine significant bias and the coefficient of repeatability of global and regional MBF and MFR measurements for the core versus local reproducibility studies and for measurements of MBF with full and half data reconstructions. The mean difference in MBF between core and local-site processing will be assessed with a paired t-test. A sample size of 25 studies per center provides 88% power (alpha=0.05) to detect a 10% difference, assuming a standard deviation in repeated MBF measurement of 15% (effect size of 0.67). Each center will recruit 5 practice patients and 25- 35 patients for analysis. There will be 6 centers and each center will recruit 30 - 40 patients for a minimum of 180 patients to a maximum of 240 patients(30 practice patients and 150 - 210 patients for analysis). Global and regional MBF at rest and stress will be separately compared. Differences in MFR will be similarly assessed.

To evaluate impact on patient throughput, the following information will be collected for each site and each MBF study:

Time patient enters the room

Time of radiotracer injection (for dynamic imaging sessions)

Start times of each image series (static and dynamic)

Time patient exits the room

Number of MPI studies done per day.

Each site will also provide number of MPI studies done per day for the 2-month period prior to starting to apply the MBF protocol and similar timing and demographic data for 25 standard (non-MBF) MPI studies.

MBF/MFR analysis will be repeated with attenuation corrected images for those data sets which include a transmission imaging.

Image quality will be assessed at the core lab. The following factors will be considered:

- Tracer bolus quality: start of bolus is imaged, bolus duration is appropriate (total activity in the FOV is within 10% of final frame value 3 minutes after start), single peak
- Positioning: Heart is within the quality FOV no truncation.

<sup>1 G\*Power software, version 3.1.3. Faul F, Erdfelder E, Lang A-G, and Buchner A. G\*Power 3: A flexible statistical power analysis program for the social, behavioral, and biomedical sciences. *Behavior Research Methods*, 39:175–191, 2007

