- Sufficient injected activity: total counts in the left ventricle in the final 2-min frame is > 1 M
- Artifacts: no evidence of patient motion (or adequate motion correction), no other visible artifacts in the images
- Number of segments with physiologically unreasonable MFR (MFR <0.8 or > 5)

MBF analysis will be repeated for the half-dose MBF data sets. Studies will be read at the Core Laboratory by two experienced readers to provide intra- and inter-observer repeatability of evaluation.

To assess the need for delayed imaging, data sets will be reprocessed at the core lab. The last 6 min of each dynamic acquisition will be used to generate a late-dynamic static MPI image series (immediate imaging). The immediate and delayed images will be reviewed blindly by two experienced readers to provide data on intra- and interobserver repeatability. The summed rest, summed stress, and summed difference scores will be recorded for a 17-segment heart model, along with a final clinical evaluation and a subjective assessment of image quality (on a scale of 1-5). All evaluations will be done by the core lab to ensure consistency in processing and evaluation.

Subjective image quality scale will be:

1 – non-diagnostic: noise or poor contrast in the myocardium prevent clinical interpretation, or artifact or extra-cardiac uptake prevent interpretation of the myocardium.

2 – poor quality: poor contrast and noise in myocardium make interpretation difficult, artifacts and extra-cardiac interference are moderate and reduce confidence in image interpretation

3 - adequate quality: adequate myocardial contrast, artifacts and extra-cardiac interference are mild and may reduce confidence in image interpretation

4 – good quality: good myocardial contrast, artifact and extra-cardiac activity may be present but do not interfere with interpretation

5 – excellent quality: good myocardial contrast, no artifacts, no interference from extra-cardiac activity

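### The core lab's full-data versus half-data MBF comparison has no blinding, although Section 5 blinds the parallel immediate/delayed reading

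*Combined protocol and SAP*

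**What the plan says.** Section 4.3 (Radiotracer) has the core lab create the half-data sets from the recordings that give the full-data result: "The listmode data from the full-dose studies with be reprocessed by the core laboratory to simulate half doses". The same section expects half doses to prove workable and gives confirmation of this as the purpose of the reprocessing. Under Section 3, the core lab also reprocesses the full data of every study.

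Section 4.5 describes the MBF step: "With this semi-automatic software, a 1-tissue-compartment model will be fit to the myocardium time-activity data". Some operator input is therefore possible.

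The criterion is the third secondary hypothesis in Section 1.2: "The difference between MBF measurements with full-data and half-data dynamic acquisitions will be less than or equal to the inter-observer variation" in full-data MBF. Section 5 assigns Bland-Altman bias and the coefficient of repeatability to the comparison, "for measurements of MBF with full and half data reconstructions". It does not say which of these is set against inter-observer variation.

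The working instruction in Section 5 is short: "MBF analysis will be repeated for the half-dose MBF data sets". The next sentence reads: "Studies will be read at the Core Laboratory by two experienced readers to provide intra- and inter-observer repeatability of evaluation". Neither sentence mentions masking, reading order or re-use of contours. The following paragraph, on a different paired comparison at the same core lab, does: "The immediate and delayed images will be reviewed blindly by two experienced readers".

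**The concern.** Two paired comparisons are made at one core lab, and only one is blinded. In the unblinded one the operator can influence the result, the partner result for the same patient is held at the same laboratory, and the protocol states which answer is expected. An operator who remembers or can look up the full-data MBF may edit the half-data processing until the two agree.

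The effect on the criterion runs one way. The benchmark contains the processing differences of two observers. Adjustment towards a known value removes part of the full-half difference and leaves the benchmark as it is. At stake is a secondary hypothesis that feeds the planning of later half-dose studies.

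**Working it through.** **Inputs from the documents.** Section 5 gives a 15% SD for repeat MBF measurement, a 10% difference, 25 studies per center, alpha 0.05, 88% power, and 150 to 210 patients for analysis. It gives no power figure for the half-data aim.

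**The plan's own figure.** For a paired t-test with n = 25 and 24 df, the noncentrality is (10/15) × √25 = 3.33, or 0.67 × 5 = 3.35. Two-sided power at 0.05 is 89.2% or 89.5%, close to the stated 88%. The figure concerns core versus local processing, so it neither supports nor refutes this point. The calculation treats 15% as the SD of a paired difference.

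**Assumptions, because the documents give no values.**
- Inter-observer difference SD: 15%, borrowed from the core-versus-local calculation.
- r: SD of the difference between two fresh processings by one reader, 8% to 15%.
- h: SD added by halving the data, 5% to 15%.
- ρ: share of operator error common to both processings, 0 to 1.
- Criterion: SD(full−half) no larger than the inter-observer SD. The plan does not define this.

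**Shared processing.** SD(full−half) = √(r²(1−ρ) + h²).

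Take r = 15%, so that a reader differs from himself or herself as much as from a colleague (15/√2 = 10.6% per reading). The chance of meeting the criterion, in brackets, was simulated with n = 150 and 20,000 runs, treating the two SDs as independent.

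| h | ρ = 1 (fully shared) | ρ = 0.5 | ρ = 0 (independent) |
|---|---|---|---|
| 5% | 5.0% (100%) | 11.7% (99.8%) | 15.8% (26%) |
| 10% | 10.0% (100%) | 14.6% (63%) | 18.0% (1.2%) |
| 15% | 15.0% (51%) | 18.4% (0.7%) | 21.2% (0%) |

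For example, with h = 10% and ρ = 0, √(225 + 100) = 18.0%.

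With r below 15% and ρ = 0, the criterion is met when h ≤ √(15² − r²):
- r = 8%: 12.7%
- r = 10%: 11.2%
- r = 12%: 9.0%

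With ρ = 1 the limit is 15% whatever r is. For r = 10% and h = 13%, the SD is √(100 + 169) = 16.4% at ρ = 0 (not met), √(50 + 169) = 14.8% at ρ = 0.5 (met) and 13.0% at ρ = 1 (met).

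**Editing towards the known value.** If the operator moves the half-data value a fraction k of the way to the full-data value, the recorded difference is (1−k) × (full − half). Both the mean difference and the SD shrink by that factor. An SD of 16.4% falls to 15% when k = 1 − 15/16.4 = 0.085. An SD of 18.0% does so when k = 1 − 15/18.0 = 0.17. Shared geometry differs: in the model above it reduces the SD but leaves the mean difference unchanged.

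**The case against.** A reader might infer that the core lab copies full-data contours, or looks at the earlier MBF, and that half dose therefore passes too easily. The documents do not support this. They say that the data are reprocessed and the analysis repeated, which fits fresh processing equally well. What stands is that nothing rules the other practice out.

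A reader might also infer that any shared geometry is a bias. That does not follow. Section 1.2 compares full-data with half-data acquisitions, and Section 5 compares reconstructions. Holding contours fixed isolates the effect of fewer counts. With ρ = 1, a limit of h = 15% is then the criterion working as one may reasonably read it. Such an analysis says nothing about extra operator error on noisier images, so its conclusion must be limited accordingly. Recall, or editing towards a known value, has no such defence.

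The two-reader sentence that follows the half-dose instruction may well cover the half-data sets, so reader repeatability on them may already be measured. It does not mask a reader to the patient's full-data result.

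The strongest practical objection is that compulsory fresh processing can defeat the criterion. If r equals the inter-observer SD, the full-half SD exceeds the benchmark for every h above zero, and the simulated chance of passing is 26% at h = 5%. This stands. It is a reason to decide on geometry and the statistic beforehand, but no reason to leave operators unmasked.

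Finally, this is a secondary hypothesis under an exploratory objective, and Section 4.3 leaves evaluation of half doses to later studies. That limits the weight of the point.

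**Conclusion.** The point holds as an unaddressed risk that is cheap to remove. The plan blinds one paired core-lab comparison and leaves its neighbour open, although that neighbour depends on an operator and the partner result is held in-house. Recall or editing towards the full-data value would favour meeting the half-data criterion.

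The documents do not give the size. The same-reader repeat SD, the SD from halving, the degree of sharing or editing, and the use of 15% as the inter-observer SD are all assumed, and the SD-against-SD criterion is one reading of an undefined rule. Within those assumptions the outcome can change. With r = 10%, sharing alters the verdict only when halving adds between 11.2% and 15%. Outside that window it does not.

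The documents do not establish that bias will occur, or that half dose would wrongly pass.

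**What to change.** In Section 5:

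1. Have full-data and half-data sets processed under coded labels, mixed in random order, without sight of any earlier MBF value for that patient.
2. State before processing starts whether geometry (contours, orientation, motion shifts) is shared or redrawn.
   - If shared, limit the conclusion to the effect of reduced counts with processing held fixed.
   - If redrawn, process each set from the start. Compare same-reader full-half differences with inter-observer differences, using one pre-stated statistic for both.

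The readers and the number of readings stay the same. The cost is protocol wording, coding of files and a little more operator time. If geometry is redrawn, same-reader repeat error enters the full-half difference. The criterion then becomes harder to meet and may fail even for a small halving effect, so the sponsor should weigh this when choosing the statistic.

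### The half-data are a subset of the full-data counts, so the spread of full minus half shows the noise added by thinning and is not a half-dose repeatability

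*Combined protocol and SAP*

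**What the plan says.** All injections in this study are at full dose (section 4.3: "For this feasibility study, full doses will be used to provide the best CFR results possible"). No separate half-dose acquisition is made. The full-dose listmode data are to be "reprocessed by the core laboratory to simulate half doses and", as the sentence continues, "confirm that half doses are adequate".

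Hypothesis b)3 in section 1.2 sets the criterion: "The difference between MBF measurements with full-data and half-data dynamic acquisitions will be less than or equal to the inter-observer variation" on full data. It gives no number for that variation and does not say whether the criterion applies to the mean difference or to its spread.

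Section 5 plans Bland-Altman bias and a coefficient of repeatability "for measurements of MBF with full and half data reconstructions". It also has two core-laboratory readers supply intra- and inter-observer repeatability. Section 2 links the half-data work to later half-dose tracer studies, and section 4.3 says that subsequent studies would evaluate half doses.

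**The concern.** The method of thinning is not described, but any half set drawn from a full-dose listmode file is contained in that file. The two MBF values being compared therefore share half of the full-data counts, and with them part of their noise. That shared part cancels in the difference.

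A future half-dose patient will have only the half-dose value, with all of its noise. If the full-half limits of agreement are read as showing how repeatable a half-dose MBF value is, they will be too narrow in their count-noise part. No other planned analysis fills the gap. Core-versus-local processing and the two-reader comparison both re-analyse the same acquisitions, and the plan has no test-retest component.

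**Working it through.** **The plan's own figure.** The documents give no power or precision for the half-dose comparison. The only power figure is 88% for core versus local MBF (section 5: n = 25 per center, 10% difference, SD 15%). A two-sided paired t-test with effect size 10/15 gives 89.2%, close to the stated value. That figure concerns another comparison and is not affected.

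**Inputs.** From the documents: nested half-data (4.3), the criterion (1.2), Bland-Altman outputs and the 15% SD (5), and frames of 9×10 s, 6×15 s and 4×120 s (4.5). Assumed: noise variance proportional to 1/counts, and a near-linear estimator. The full-data count-noise SD, s, is not given.

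**Count-noise algebra.** Let a and b be the MBF estimates from two complementary halves. They are independent, each with variance 2s². Full data is F ≈ (a + b)/2, with variance (2s² + 2s²)/4 = s².

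| Quantity | Variance | SD |
|---|---|---|
| Nested: F − a ≈ (b − a)/2 | 4s²/4 = s² | 1.00s |
| One half-dose value | 2s² | 1.41s |
| Two independent full-dose values | s² + s² = 2s² | 1.41s |
| Independent full versus half | s² + 2s² = 3s² | 1.73s |
| Two half-dose values: a − b | 2s² + 2s² = 4s² | 2.00s |

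The nested SD is 1/1.41 = 71% of half-dose noise, 1/1.73 = 58% of the independent full-versus-half SD, and 1/2.00 = 50% of the half-versus-half SD.

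**Simulation.** Poisson thinning with 400,000 replicates gave 1.001 (nested), 1.416 (half alone), 1.732 (independent) and 2.002 (half versus half). A one-tissue-compartment fit on the protocol's frames, with an assumed input function and K1 and 20,000 replicates at each of three count levels, gave 1.01–1.06, 1.41–1.49 and 1.74–1.80 for the first three. Full-data CV ran from 1.2% to 7.5%. The ratios survive the kinetic fit. The simulation did not include MLEM with a noise-suppression prior, which may shift them.

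**Mean difference.** The expected value of F − a does not depend on whether counts are shared, so the nested comparison is sound for bias.

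**Adding operator variation.** If the reprocessing difference has SD r, the ratio of planned to independent SD is √(r² + s²)/√(r² + 3s²). Taking r = 15% (section 5's SD, used here as an assumption) and the simulated range of s:

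- s = 1.2%: √(225 + 1.44)/√(225 + 4.32) = 15.0/15.1 = 0.99
- s = 7.5%: √(225 + 56.25)/√(225 + 168.75) = 16.8/19.8 = 0.85
- r = 0: 1/√3 = 0.58

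**What a spread criterion would accept, at the r = 0 limit.** The documents give no inter-observer SD, so a range is assumed.

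| Inter-observer SD (assumed) | Nested passes for s up to | Half-dose noise within margin for s up to | Independent full-half within margin for s up to |
|---|---|---|---|
| 5% | 5% | 5/1.41 = 3.5% | 5/1.73 = 2.9% |
| 10% | 10% | 7.1% | 5.8% |
| 15% | 15% | 10.6% | 8.7% |

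**The case against.** The strongest reply is that the plan's comparison answers the question it poses. Hypothesis b)3 asks what halving the data changes. The nested variance is exactly the added noise, 2s² − s² = s², and the plan nowhere calls it the total noise of a half-dose value. That stands, and it is why the point concerns how the spread is labelled and used.

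Several stronger readings are tempting but not supported:

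- **That half dose will pass too easily.** Shared counts leave the mean unbiased, and section 1.2 does not say that spread is the criterion. The inter-observer margin comes from readers of the same acquisition and so holds little or no count noise. That makes the margin smaller and the test stricter. The software is semi-automatic (section 4.5), so unless contours are carried over, reprocessing variation enters the full-half difference and could make a spread criterion fail even when thinning adds little.
- **That 58% is the general size.** It is the limit with no operator variation; the illustration above gives 0.85 to 0.99 when r is 15%.
- **That this result fixes the dose of later studies.** Section 4.3 says only that they would evaluate half doses. No decision rule is attached, and section 2 presents the work as exploring optimization.
- **That half-versus-half repeatability should be the sole test of b)3.** Two independent full-dose values would already differ with SD 1.41s, so full dose itself might fail the same margin.

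It can also be said that doubling the planned SD gives the half-versus-half figure with no new work. Under exact linearity and no operator variation it would. MLEM with a prior is non-linear, however, and operator variation does not scale with counts, so doubling is not a substitute.

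**Conclusion.** The point holds for spread and not for bias. The full-half coefficient of repeatability and limits of agreement measure the noise added by thinning plus any reprocessing variation. They understate the disagreement expected between separate full-dose and half-dose acquisitions, and they are not a half-dose repeatability.

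The understatement in SD lies between a ratio of 0.58, when operator variation is negligible, and close to 1, when it dominates. The documents give neither component, so the size in this trial is unknown. The result rests on noise variance proportional to 1/counts and a near-linear estimator. Whether it affects the conclusion on b)3 depends on a choice the plan has not made, between mean and spread. This is a measurement point on a secondary hypothesis. It takes no position on which dose is right and leaves the primary comparison untouched.

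**What to change.** 1. Split each listmode file into two complementary, non-overlapping halves, A and B, and reconstruct and fit both.
2. Use the mean of full minus half for bias, as planned.
3. Report the A-versus-B coefficient of repeatability beside inter-observer variation, described as within-acquisition count-noise repeatability at half data. Note that both halves share one injection, bolus, position and motion, so it is not a full test-retest figure.
4. Label the full-half limits of agreement as added noise only, and do not use their spread alone to conclude that half doses are adequate.
5. State in section 1.2 or section 5 whether b)3 is judged on mean or spread.

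The cost is one extra reconstruction and kinetic fit per scan, on data already held, with no patient contact and no added activity. The drawback is core-laboratory time and a less favourable repeatability figure.
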